6.4.1 Visit 9 (Week 12 and taper)

The study nurse will dispense study medications as shown in Table 1. At this visit (+/- 4 days), the subject will receive 1 more week of 100 mg BID (enough study medication to complete a total of 84 days on study medication) and the 6-day study medication taper (to reduce the dose by 50 mg every 2 days over 6 days: 150 mg for 2 days, 100 mg for 2 days, 50 mg for 2 days, then discontinue it). In the event that scheduled visits change or the subject's dosage is adjusted by the study physician, medication will be mailed via a UPS or Fedex to the subject, to ensure that they have enough medication to get them to their next scheduled visit. The study physician will approve all medication mailed to subjects and the study nurse or physician will document the medication dispensed via mail and call to instruct the subject on how the medication should be taken and to document all AEs. Study staff will also document whether mailed medication was received by the subject.

At this visit, the subject's BrAC, weight, and vital signs will be measured. Subjects will be asked not to drink before coming to the scheduled visits. Subjects will be asked to complete a breathalyzer test. If a subject's breath alcohol concentration is $\geq 0.02\%$, an investigator will evaluate whether the subject is too impaired to complete the study assessments. The study visit may be completed at the discretion of the investigator. If the subject is deemed to be unable to complete assessments, the investigator may ask the subject to wait until his or her blood alcohol level decreases or if that is not feasible to return the next day after having consumed no alcohol. Prior to discharge from the TRC, a clinician will assess the subject to ensure that it is safe for the subject to leave. Study staff will complete the following assessments with all subjects (the exception being that only for women of childbearing potential, will study staff obtain a urine sample for a pregnancy test). Subjects who are deemed suitable for assessment will then complete questionnaires and be interviewed by the study nurse about their concomitant medications, adverse events, protocol compliance, and MM intervention. For women of childbearing potential, study staff will obtain a urine sample for a pregnancy test.

Study staff will also administer the following assessments, as described above:

- *The Timeline Follow-back (TLFB)*: To collect data on daily drinking, cigarette use, and medication taken.

CONFIDENTIAL

- *The Patient Health Questionnaire (PHQ-9)*: To measure depressive symptoms.
- *The International Neuropsychiatric Interview 6.0 (Mini 6)*: Suicidal risk will be assessed using the MINI Suicidality section (B) and, if rated greater or equal to 9 (i.e., clinically significant suicidal ideation), the physician will be consulted to decide on the appropriate clinical management.
- *The Clinical Institute Withdrawal Assessment for Alcohol Scale–revised (CIWA-Ar)* (Sullivan, Sykora et al. 1989) is a 10-item scale for clinical quantification of the severity of alcohol withdrawal.
- *Medication Adverse Effects Checklist*
- *Measures of treatment received*
- *Daily Interactive Voice Response Telephone Call (daily for 12 weeks, beginning with the initiation of treatment)*
- *ISI*

6.5 Visit 10 (Week 13; Endpoint Visit)

At the end of treatment, week 13 (+/- 4 days) we will repeat the research assessments and will query the subject as to his or her belief regarding their treatment condition using the Medication Questionnaire (MED-Q). Blood samples for measurement of serum GGTP and %dCDT will be obtained to assess the validity of self-reported drinking. Subjects will be asked not to drink before coming to the scheduled visits. Subjects will be asked to complete a breathalyzer test. If a subject's breath alcohol concentration is $\geq 0.02\%$, an investigator will evaluate whether the subject is too impaired to complete the study assessments. The study visit may be completed at the discretion of the investigator. If the subject is deemed to be unable to complete assessments, the investigator may ask the subject to wait until his or her blood alcohol level decreases or if that is not feasible to return the next day after having consumed no alcohol. Prior to discharge from the TRC, a clinician will assess the subject to ensure that it is safe for the subject to leave. Study staff will complete the following assessments with all subjects (the exception being that only for women of childbearing potential, will study staff obtain a urine sample for a pregnancy test). Subjects who are suitable for assessment will then complete questionnaires and be interviewed by the study nurse.

All subjects will be asked to complete an end-of-treatment evaluation and to complete all scheduled assessments to facilitate intent-to-treat (ITT) analyses. All subjects will be informed of these procedures prior to study enrollment. Subjects will be compensated \$50 for completing the end-of-treatment visit. Subjects who decide to terminate the study prior to visit 10 will also receive payment upon completion of the end-of-treatment procedures and 3- & 6-month follow-up visits. For subjects who withdraw early and do not wish to continue with study visits/procedures, all end-of-treatment procedures will be administered at the time of withdrawal. These subjects will also be asked to undergo in-person or telephone follow-up at the end-of-treatment for collection of the remaining treatment-phase Timeline Follow-back data.

If the subject cannot be reached by phone after three attempts, a final outreach letter will be mailed. The study nurse and physician will follow continuing adverse events to their conclusion, as feasible. Subjects requesting (or clearly needing) additional treatment for alcohol problems will be referred to local treatment centers.

CONFIDENTIAL

- Breathalyzer, weight, and vital signs
- Timeline Follow-back (TLFB) interview
- The International Neuropsychiatric Interview 6.0 (Mini 6): Suicidal risk will be assessed using the MINI Suicidality section (B) at each study visit and, if rated greater or equal to 9 (i.e., clinically significant suicidal ideation), the physician will be consulted to decide on the appropriate clinical management.
- The Clinical Institute Withdrawal Assessment for Alcohol Scale–revised (CIWA-Ar)
- The Patient Health Questionnaire (PHQ-9)
- Word Association Test (COWA)
- Wechsler Adult Intelligence Scale-Third Edition Digit Span subtest
- Alcohol Urge Questionnaire (AUQ)
- Fagerstrom Test for Nicotine Dependence (FTND)
- Medical Management
- Medication Adverse Effects Checklist
- Measures of Treatment Received
- Medication Questionnaire (MED-Q)
- Short Index of Problems (SIP)
- RAND 12-Item Health Survey (SF-12)
- DSM-5 AUD Diagnosis (using the SCID for DSM-IV adapted for this purpose)
- Early Termination Form (for early withdrawal from the study) indicates the subject's level of functioning at termination, and will be completed by the study staff or study nurse for any subjects that leave treatment prematurely. The form is used to identify the reasons for early termination (e.g., symptomatic failure, adverse effects) and other relevant circumstances.
- ISI

6.6 Missed Visit

Subjects will receive study medication from the study nurse or physician at each study visit. During the first 6 weeks they will receive 8 days of study medication, which is enough medication to get them to their next scheduled study visit, plus 1 extra day. Once the subject reaches the 200 mg daily dose, they will receive 16 days of study medication, which is enough to get them to their next scheduled study visit plus 2 extra days. The study coordinator will work with the study nurse to ensure that the treatment phase of the study is not extended beyond 12 weeks. At visit 9, the study nurse will dispense the exact amount of study medication required for the subject to complete 84 days of study medication before starting the taper. These procedures will ensure that no subject is on study medication for more than 84 days before tapering off the study medication.

If a subject anticipates missing a study visit (e.g., due to a vacation), the study nurse will provide the subject with enough study medication to ensure that the maintenance of the daily dosage of study medication until the next scheduled visit. In the event that study medication is not ready to be dispensed at the time of the study visit (e.g., nurse and/or physician determine at the time of

CONFIDENTIAL

the study visit that the subject requires a reduced dosage), study staff will mail the study medication to the subject via UPS or Fedex, to ensure that they have enough medication to get them to their next scheduled visit. The study physician will approve all medication mailed to subjects and the study nurse or physician will document the medication dispensed via mail. The study nurse will call the subject to document that all mailed study medication was received by subjects, to provide instructions on how to take the study medication as per the dosing schedule, and to collect information on any AEs. Subjects will be instructed to call the Treatment Research Center (TRC) at any time to discuss problems or concerns they may have while participating in the study. They will be provided phone numbers to contact the study staff during office hours and a pager number for off-hours contact. Subjects will be asked to come in for their next study visit as soon as possible.

If a subject anticipates missing a study visit (e.g., due to vacation), the study staff and study nurse will attempt to schedule a day and time to conduct the study visit over the phone for safety monitoring and data collection purposes. Self-report assessments, completed by subjects at study visits, will be administered by study staff over the phone. Breathalyzer, weight, and vital signs will not be obtained for phone visits. Subjects will be compensated for completing phone visits at their next study visit. If a subject is traveling out of the range of telephone access (e.g., internationally), he or she will be provided with paper copies of the daily IVR diary report to complete each evening instead of calling in to the system. The subject will be compensated for completing the IVR report on paper at their next study visit.

If a subject calls to cancel a scheduled study visit due to an unforeseen event, the study visit will be rescheduled for as soon thereafter as possible. Study staff will mail study medication to the subject via UPS or Fedex, under the supervision of a study nurse to avoid having the subject run out of study medication. Subjects will be given only enough study medication to ensure that they maintain their daily dosage of study medication until their next scheduled visit. The physician or nurse will instruct the subject by phone regarding how to take the study medication per the dosing schedule and will record any adverse events that have occurred since the last study visit. Study nurses will instruct subjects to call the TRC at any time to discuss any problems or concerns they may have while taking the study medication. Study staff will also document whether the mailed medication was received by the subject. Study staff will make efforts to reschedule missed study visits as soon as possible. The study physician will approve all medication mailed to subjects and determine how many additional weeks of study medication a subject will be allowed to receive without attending a study visit.

6.8 Visits 11 and 12 (Weeks 24 and 36; Post-treatment Follow-up Visits)

- At the 3-month and 6-month follow-up visits, we will repeat the research assessment, focusing principally on alcohol consumption and alcohol-related problems over the preceding 12 weeks (or for individuals for whom data are missing, we will attempt to have them reconstruct their drinking history since the last assessment was completed). We will also obtain a blood sample for measurement of serum GGTP and %dCDT to assess the validity of self-reported drinking.
- Subjects will be asked not to drink before coming to the scheduled visits. Subjects will be asked to complete a breathalyzer test. If a subject's breath alcohol concentration is \geq 0.02%, an investigator will evaluate whether the subject is too impaired to complete the study assessments. The study visit may be completed at the discretion of the investigator. If the subject is deemed to be unable to complete assessments, the investigator may ask the subject to wait until his or her blood alcohol level decreases or if that is not feasible to return the next day after having consumed no alcohol. Prior to

CONFIDENTIAL

discharge from the TRC, a clinician will assess the subject to ensure that it is safe for the subject to leave.

- After the six-month follow-up visit, subjects who wish to learn whether they received treatment with topiramate or placebo will receive a “de-briefing letter” from IDS. Subjects will have the option to receive the “de-briefing letter” at the screening visit by initialing yes on the ICF. Study staff will provide IDS with an envelope that has the patient’s address along with the “de-briefing letter,” which notes the patient’s name and ID number. The pharmacy technician will complete the letter indicating the medication assignment, and mail it to the subject. Study staff (physicians, nurses, and coordinators) will remain blinded to study medication assignment.
- Breathalyzer, weight and vital signs
- Medication Adverse Effects Checklist (Follow-up with any unresolved AEs)
- Timeline Follow Back (TLFB)
- The International Neuropsychiatric Interview 6.0 (Mini 6): Suicidal risk will be assessed using the MINI Suicidality section (B) at each study visit and, if rated greater or equal to 9 (i.e., clinically significant suicidal ideation), the physician will be consulted to decide on the appropriate clinical management.
- Word Association Test (COWA)
- Wechsler Adult Intelligence Scale-Third Edition Digit Span subtest
- Alcohol Urge Questionnaire (AUQ) Fagerstrom Test for Nicotine Dependence (FTND)
- SCID module for the AUD diagnosis (adapted from DSM-IV to yield a DSM-5 AUD Diagnosis)
- Short Index of Problems (SIP)
- The Patient Health Questionnaire (PHQ-9)
- RAND 12-Item Health Survey (SF-12)
- Measure of treatment received
- ISI

6.9 Description of Study Treatments

6.9.1 Pharmacotherapy:

The maximal dosage of topiramate to be used in the present study is 200 mg/day in two divided doses. We will use a six-week titration period, which was well tolerated in our completed topiramate study. The dosage of medication (active or placebo) will be increased only as tolerated and subjects experiencing intolerable adverse effects will have their dosage decreased gradually to the highest tolerated dosage, which will be determined by the study physician. The study nurse, in consultation with the study physician, will provide guidance for subjects as they increase their medication dosage, per the titration schedule.

CONFIDENTIAL

6.9.2 Medical Management Counseling:

At each treatment visit, all subjects will receive medical management (MM), a standard, widely used, medically oriented intervention that supports the use of pharmacotherapy and enhances medication adherence in the treatment of AUD (Pettinati, Weiss et al. 2004). Clinicians with minimal specialty training but who are knowledgeable about AUD can deliver this brief and effective intervention, which has been widely used. In MM, the clinician highlights the individual's AUD symptoms and need for treatment. The subject is advised to reduce or stop drinking, is educated about AUD, is provided a rationale to take medication for its treatment, and is instructed on the importance of daily medication adherence. The clinician and subject jointly develop an individualized medication adherence plan and the subject is given information on the medications. MM enhances adherence and provides treatment that is feasible in most medical settings, but unlikely to obscure a medication effect on drinking outcomes.

Subjects will receive MM at each of the treatment visits. The first MM session will last 30 minutes and subsequent sessions 20 minutes. During all sessions, the study nurse will check the subject's vital signs and weight, adverse effects, medication adherence, and concurrent medications; and make recommendations for the subject to follow until the next visit. Individuals with severe psychological symptoms (e.g., suicidal thoughts) will be withdrawn from treatment and referred for appropriate clinical care. Suicidal risks will be assessed using the MINI Suicidality section (B) at each study visit, and if rated equal to or greater than 9 (i.e., clinically significant suicidal ideation), the physician will be consulted to decide the appropriate clinical management.

Ensuring Adherence to MM Content and Procedures: [name], MSN, CRNP, nurse practitioner, has more than 10 years of experience with MM (Pettinati, Weiss et al. 2004), including in the completed topiramate trial (Kranzler, Covault et al. 2014). She will train the other nurses in its administration, which will entail a review of the protocol and MM manual, role-play, practice of initial and follow-up sessions, and review of taped practice sessions until adequate performance is achieved. To assure the quality and uniformity of all sessions, audiotapes (with the consent of the participant) will be used to monitor the MM sessions for this study. The audiotapes will be reviewed by a trained clinician not involved in the counseling process. S/he will listen to 10% of recorded visits and will evaluate adherence to MM principles, record the total time in the treatment session, assess the therapeutic relationship, review the achievement of reduced drinking goals and clinical improvement during treatment, and provide individual feedback. One session from each subject will be reviewed with equal frequency for each of the nine different MM sessions. Weekly protocol adherence meetings will be held with the study nurses to assure protocol adherence. Audiotapes will be destroyed after review.

6.10 Description of Laboratory/Medical Assessments:

These assessments serve to: 1) screen subjects for medical exclusion criteria, 2) assess potential adverse effects of topiramate, and 3) corroborate self-reported drinking. Prior to entrance into the study, each subject will receive a physical exam, urinalysis and urine toxicology, CBC, a chemistry panel [which includes electrolytes, liver enzymes (ASAT, ALAT, GGTP), bilirubin, uric acid, BUN, and creatinine], %dCDT, and pregnancy testing for women of childbearing potential. Bicarbonate levels will be repeated at the week six visit because topiramate can cause metabolic acidosis. Pregnancy testing for women of childbearing potential will also be repeated at visits 1 (week 1), 5 (week 5), 7 (week 8), and 9 (week 11). If a subject reports being pregnant or tests positive, she will immediately be excluded or withdrawn from treatment with medication, referred for obstetric evaluation, and advised to discontinue all drinking. At the week six visit and endpoint, GGTP and %dCDT will be repeated to corroborate self-reported alcohol consumption. %dCDT will be measured in the laboratory of [name]

CONFIDENTIAL

[name], using the HPLC reference assay method, recommended for the measurement of %dCDT, the new standard analyte for measurement of CDT. This method corrects for total transferrin concentration and increases the utility of CDT to evaluate heavy drinking in women (Helander, Wielders et al. 2010).

6.11 Study Timeline:

Table 3: Timeline of Performance Goals

Activity	Year 1	Year 2	Year 3	Year 4	Year 5
Staff training & study preparation	■				
Subject enrollment	■	■	■	■	■
Endpoint assessments	■	■	■	■	■
Data entry & cleaning	■	■	■	■	■
Data analysis				■	■
Report writing				■	■

7 Statistical Plan

7.1 Sample Size Determination

Power for the analysis for **Specific Aim 1**, as described below, will be determined by the patterns of outcomes in the final six weeks, so power estimates are based on weeks 7 through 12 as a 6-week trial, with adjustments for loss to attrition between baseline and week 6. Based on our prior study (Kranzler, Covault et al. 2014), we anticipate that, through the first six weeks, 94% of subjects (i.e., n=47 per group) will provide data, despite up to 10% discontinuing medication. We anticipate an additional 6% loss due to dropout from research during the final six weeks, also with 10% discontinuing treatment. In these power estimates, we use a square root transform to approximate the Poisson distributions by Normal distributions, on which we base our estimates using the methods of Hedeker et al. (1995) and Stroup (1999). Our primary comparison is the interaction effect of *GRIK1* with TOP. In our previous study, for the square root Poisson scale, we observed a standardized effect (Cohen 1988) of d=0.27 for TOP relative to PLA in the AA/AC group and a standardized effect of d=0.93 for TOP relative to PLA in the CC group. We have a single primary hypothesis, so we consider power for a two-sided test at $\alpha=0.05$, with a total of $4 \times 47=188$ subjects, with 6% research loss to attrition across six weeks. Finally, we assume a within-subject correlation of 0.35 for the repeated measures. With these assumptions, we have 81% power for the effects observed in our prior study. For **Specific Aim 2**, we used simulation studies (Kreft and De Leeuw 1998) to evaluate the adequacy of our sample size in relation to moderation by the CC genotype of TOP's effects on the contingent relation between early evening outcome expectancies and nighttime drinking (Kranzler, Armeli, et al. 2013). These show that designs having at least 30 level-2 units with 30 observations each (i.e., 900 total person days) will provide power of 80% to detect small effect sizes. Assuming a rate of missing data of about 20% (Kranzler, Armeli, et al. 2013), we will have approximately 15,000 person days for the comparison of TOP and PLA, which will provide high power to detect a small effect.

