Our primary hypothesis is that the effect will be significantly larger in rs2832407 C-allele homozygotes than in A-allele carriers. We will also examine the SNP's moderating effects on the efficacy of topiramate in improving other self-reported drinking measures (e.g., abstinent days), adverse consequences of drinking (e.g., the Short Index of Problems score: SIP; see section 6.8.3 below), and biological measures of heavy drinking (e.g., %dCDT, an improved assay for carbohydrate deficient transferrin). Finally, we will conduct 3- and 6-month post-treatment assessments on the hypothesis that rs2832407 C-allele homozygotes will show greater reduction in primary and secondary outcomes after the medication is discontinued.

The primary outcome for the study is the frequency of heavy drinking (defined as 4 or more drinks in a day for women and five or more drinks in a day for men).

Secondary outcomes include the number of abstinent days, absence of any heavy drinking days during the last month of treatment, mean daily alcohol consumption, drinks/drinking day, %dCDT and gamma glutamyl transpeptidase (GGTP) levels, and severity of alcohol-related problems (i.e., SIP score), using models similar to those described below for the primary outcome.

2.2. Secondary Objective: To examine daily processes, including expectancies regarding the positive effects of drinking and confidence in resisting heavy drinking and their interaction with genotype and medication group to predict the intensity of nighttime drinking. We expect that evening reports of a high level of positive expectations regarding alcohol's effects and a low level of confidence in resisting heavy drinking will be associated with heavier drinking later that night.

Our secondary hypotheses are that topiramate treatment will significantly reduce both positive alcohol-outcome expectancies and confidence in resisting heavy drinking across the weeks of the study and nighttime drinking measured daily in rs2832407 C-allele homozygotes, but not A-allele carriers.

2.3 Optional MRI Sub-Study Objective: Conduct an optional sub-study to examine the effects of topiramate on resting baseline (RB) cerebral blood flow and alcohol cue reactivity using functional magnetic resonance imaging (fMRI). The goals, rationale, background and study methods for this objective are described in Appendix I: "Brain Mechanisms of Topiramate's Effects on Heavy Drinking."

3 Study Design

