Multilevel models similar to those described above will be used to evaluate the associations between alcohol expectancies and daily drinking and how these associations vary as a function of medication group and rs2832407 genotype. Similar to Kranzler et al. (2013), we will focus on predicting nighttime drinking (i.e., drinks consumed after the early evening report), but here we will use alcohol-related expectancies reported during the early evening in the daily survey. Nighttime drinking levels will be determined by subtracting the number of drinks consumed during the current day from the total number of drinks consumed for that day (reported the following day). We will follow the general analysis scheme used by Kranzler, Armeli et al (2013), but will use mixed effects/multilevel models, rather than generalized estimating equations (GEE) models (Walls, Jung et al. 2006, Schafer 2006). We will examine the number of drinks consumed (using a Poisson model). We will use the HGLM module of the HLM7 program, as it is more flexible for some of our models than PROC GLIMMIX in SAS. Analysis will focus on the last six weeks of treatment, consistent with the analyses of the primary outcome in Specific Aim 1.

Predictors in these models will include 6 day-of-the-week contrasts in the level-1 model (i.e., including responses that change over days within person), to control for day of the week trending in the outcomes [e.g., greater propensity to drink on weekends (Armeli, Carney et al. 2000, Armeli, Tennen et al. 2000)], along with linear and quadratic study time contrasts and daytime drinking. The day-level predictor of interest (i.e., expectation of positive effects of drinking) will also be included in the level-1 portion of the model. The outcome expectancy

CONFIDENTIAL

predictor will be person-mean centered (91). The level-2 portion of the model (i.e., measures that do not change over days) will include treatment group, binary factors for rs2832407 genotype (i.e., CC vs. A-carrier) and associated interaction terms. This analysis will test the hypothesis that TOP will significantly reduce positive alcohol expectancies relative to PLA, but only in C-allele homozygotes, similar to the analysis of the primary outcome in Specific Aim 1.

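### Aim 2's high power for a small effect is inferred from person-days, but its hypotheses are medication-by-genotype effects that vary only between persons, and the plan does not support that power for them

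*Combined protocol and SAP*

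**What the plan says.** Section 7.1 (Sample Size Determination) judges the sample size for Aim 2 against "moderation by the CC genotype of TOP's effects on the contingent relation between early evening outcome expectancies and nighttime drinking". It cites simulation work under which "designs having at least 30 level-2 units with 30 observations each (i.e., 900 total person days) will provide power of 80" per cent for small effects. It then allows for about 20% missing reports and concludes: "we will have approximately 15,000 person days for the comparison of TOP and PLA", "which will provide high power to detect a small effect".

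The hypotheses are stated elsewhere. Section 2.2 expects topiramate to change expectancies, confidence in resisting heavy drinking, and "nighttime drinking measured daily in rs2832407 C-allele homozygotes, but not A-allele carriers". Section 7.2 says the analysis tests whether "TOP will significantly reduce positive alcohol expectancies relative to PLA, but only in C-allele homozygotes". The same section puts treatment group, genotype and their interaction at level 2 (the person), makes the expectancy predictor a day-level, person-mean-centred variable, and focuses the analysis on the last six weeks.

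For Aim 2 the plan does not define a small effect, and it gives no within-person correlation for daily data, no random-slope variance and no cell sizes.

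**The concern.** Within the power paragraph the target moves from genotype moderation to topiramate against placebo, and the unit of information moves from persons to person-days. More days per person sharpen each person's mean or slope. They do not reduce the variation between persons, and medication and genotype differ only between persons. A count of person-days therefore cannot by itself establish power for a four-cell contrast of persons.

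If the claim stands, a null moderation result in Aim 2 could be taken as good evidence that genotype does not matter, when the test may have had little chance of finding a small effect.

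**Working it through.** **Inputs from the documents.** 200 randomized (Study Summary), 100 per arm (5.3), and comparable numbers in the four medication-by-genotype groups (3.1), so 200/4 = 50 per cell; 47 per cell after attrition to week 6 (7.1). Daily reports for 12 weeks = 84 days (6.3). Aim 2 window of six weeks = 42 days (7.2); with 20% missing, 42 × 0.8 = 33.6, so m = 34 reports per person. Correlation 0.35, stated in 7.1 for the Aim 1 repeated measures only.

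**Assumptions.** Two-sided 5% test, as for Aim 1; normal approximation; a small effect taken as 0.2 SD for person-level contrasts and as 0.1 or 0.2 for slopes; correlation varied from 0.1 to 1.

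**1. The plan's person-days.** 200 × 84 × 0.8 = 13,440, not 15,000. In the six-week window, 200 × 42 × 0.8 = 6,720. The count comes near 15,000 only with 10% missing (200 × 84 × 0.9 = 15,120) or 13 weeks (200 × 91 × 0.8 = 14,560), neither of which is stated.

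**2. The plan's 80% at 30 persons × 30 days.** The simulation inputs are not given, so the figure cannot be reproduced. Treating 900 days as independent, a correlation of 0.10 has SE 1/√897 = 0.033 on the Fisher scale and power 85%. For the four-cell contrasts, 30 persons means 7.5 per cell:
- Slope contrast with no slope variation between persons, the best case: SE = √(4 × (1/30)/7.5) = 0.133. Power is 32% for a difference of 0.2 and 12% for 0.1.
- Person-level contrast at correlation 0.35: SE = √(4 × (0.35 + 0.65/30)/7.5) = 0.445. Power is 7% for 0.2 SD.

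**3. Person-level hypotheses in the full trial.** The variance of a person's mean, in total daily variance units, is v = ρ + (1 − ρ)/m. The interaction has SE = √(4v/n), with n per cell. Topiramate against placebo has SE = √(4v/200). With n = 50, m = 34 and a difference of 0.2:

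| ρ | v | SE, interaction | Power, interaction | Power, topiramate vs placebo |
|---|---|---|---|---|
| 1 | 1.000 | 0.283 | 11% | 29% |
| 0.5 | 0.515 | 0.203 | 17% | 50% |
| 0.35 | 0.369 | 0.172 | 21% | 64% |
| 0.2 | 0.224 | 0.134 | 32% | 85% |
| 0.1 | 0.126 | 0.101 | 51% | 98% |

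With n = 47 the interaction powers are 11%, 16%, 20%, 31% and 49%. The difference detectable with 80% power at ρ = 0.35 is 2.80 × 0.172 = 0.48 SD (n = 50), or 0.50 SD (n = 47).

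**4. Slope moderation in the full trial.** Let τ be the SD of slopes between persons, in units of within-person residual SD per within-person SD of expectancy. SE = √(4(τ² + 1/m)/n). With n = 50 and m = 34:

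| τ | SE | Power, difference 0.2 | Power, difference 0.1 |
|---|---|---|---|
| 0 | 0.049 | 98% | 54% |
| 0.2 | 0.075 | 77% | 27% |
| 0.5 | 0.150 | 27% | 10% |

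**5. Cross-check against Aim 1.** Section 7.1 reports 81% power for the medication-by-genotype contrast at 0.93 − 0.27 = 0.66 SD. That implies SE = 0.66/(1.96 + 0.88) = 0.233, and hence about 14% power at 0.2 SD. This is a benchmark only. Simple formulas with n = 47 give 92% if the six weeks are averaged and 62% if they are not, so the 81% is not matched exactly either.

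**The case against.** The strongest reply is that the effect named in the 7.1 power text is a cross-level slope moderation. Days do add information there, through the 1/m term. Section 7.2 starts from a random intercept and adds random slopes only if needed, so a small τ is not ruled out, and with τ near 0 a slope difference of 0.2 has 98% power. This stands. It means that power for the slope test is undetermined, not that it is low.

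It also stands that 0.35 was given for Aim 1, that small is undefined, and that a low daily correlation helps: at 0.1 the interaction reaches 51%. The closing sentence of 7.1 refers literally to topiramate against placebo, for which power is far better than for the interaction (64% at 0.35, 98% at 0.1). Aim 2 is also a secondary objective.

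Three stronger readings are tempting, and the documents do not support them:
- A reader might infer that Aim 2 as a whole has 11–32% power. That range covers only the person-level contrasts, at correlations from 1 to 0.2.
- A reader might infer a detectable slope difference of 0.79 slope SD (2.80 × 0.283). That is the floor with unlimited days. With 34 reports it is about 0.84 at τ = 0.5 (2.80 × 0.150/0.5) and 1.04 at τ = 0.2 (2.80 × 0.0745/0.2).
- A reader might infer that the 30 × 30 rule is known to be a rule for within-person effects. The 85% in step 2 is suggestive, but what the cited simulations modelled is not in the documents.

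None of this rescues the claim. The 30 × 30 benchmark does not reach 80% for the four-cell slope contrast at either assumed size even in its best case, and the person-level hypotheses in 2.2 and 7.2 gain little from extra days.

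**Conclusion.** The concern holds for the medication-by-genotype hypotheses. High power for a small effect is not supported for the tests it is offered for.

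For the person-level hypotheses, power is about 21% at 0.2 SD if the Aim 1 correlation carries over, and it does not exceed 51% for correlations of 0.1 or more. For the slope moderation it is high only if the slope difference is near 0.2 and slopes vary little between persons. The plan states neither condition.

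These figures rest on 0.2 SD (or 0.1 to 0.2 for slopes) as the meaning of small, 34 reports per person, about 50 persons per cell and a normal approximation to outcomes that, for drinks, will be modelled as Poisson. The shortfall in person-days is a separate and lesser error; the main point does not depend on it.

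**What to change.** In section 7.1, replace the person-day statement for Aim 2 with power, or the detectable difference, for the medication-by-genotype contrast on 188 to 200 persons over the six-week analysis window. Give the person-level and the slope hypotheses separately. State the assumed effect size, daily within-person correlation and random-slope variance, each with a range. Correct the person-days to about 6,720 for that window (13,440 over the full 12 weeks). Keep the claim of high power for a small effect only for within-person associations pooled over groups. Do not print 0.79 slope SD, or 11–32% as the power for all of Aim 2.

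The cost is one rewritten paragraph and a less favourable stated figure. Recruitment, visits and data collection do not change.
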